7.4 Exit Visit or Early Termination Visit

7.4.1 Visit V5 (week 14 or two weeks after the last dose of investigational product if a subject early terminates)

At the V5 visit the study investigator will:

- Review SMBG and glycemic control record
- Perform a complete physical examination including weight
- Measure vital signs, including blood pressures, pulse, temperature, and respiratory rate
- Perform a 12-lead ECG measurement
- Draw blood from subjects who have fasted a minimum of 10 h as described in [Section 6.7.2.1](#). The specific laboratory tests scheduled for this visit are listed in [Appendix 2](#)
- Collect clean-catch, mid-stream urine sample for urinalysis in all subjects and for UPT for women of child bearing potential
- Assess adverse events and record concomitant medications: If subjects have an ongoing serious adverse event, the subject should be followed until the adverse event is resolved or returns to baseline. All possible attempts should be made to document resolution of acute and chronic toxicities.

7.5 Early Termination Procedures

Subjects removed from the study due to drug related toxicity will be followed until resolution or stabilization of the adverse event. The sponsor must be notified in the event that a subject withdraws or has been withdrawn from the study.

Subjects who withdraw consent and have received investigational product will have a follow-up examination, including a complete physical examination, vital signs, ECG, and clinical laboratory tests (hematology, serum chemistry, and glycemic control).

8 QUALITY CONTROL AND ASSURANCE

The clinical research facility will be monitored by the study monitor to ensure correct performance of the study procedures and to ensure that the study is conducted according to the protocol and relevant regulatory requirements. CRF entries will be verified with the source documentation.

Quality control principles will be applied throughout the performance of this study by following the SOPs of the CRO and the sponsor. Review procedures will be implemented at the CRO for all documents that are generated in relation to the study.

9 PLANNED STATISTICAL METHODS

9.1 General Considerations

All statistical analyses will be performed using Version 9.4 or later of Statistical Analysis Software (SAS®).

Data summaries will use descriptive statistics (number of subjects [n], mean, standard deviation [SD], Q1, median, Q3, minimum, and maximum) for continuous variables, and frequency and percentage for categorical and ordinal variables. If there are missing values, the number missing will be presented, but without a percentage. All data collected will be included in by-subject data listings.

Unless otherwise specified, all tests will be two-tailed using a 0.05 level of significance. All confidence intervals (CIs) will be two-sided 95% confidence intervals.

9.1.1 Handling Dropouts, and Missing Data

Discontinuation criteria are explained in [Section 6.12](#). Subjects who discontinue will not be replaced. To the extent possible, attempts will be made to minimize the amount of missing data through measures planned in the study conduct. But if missing data are present for the primary efficacy endpoint, they will be handled using a multiple imputation approach. The imputation method is as follows:

As the primary analysis, only available data will be analyzed and data obtained after rescue will be excluded and considered as missing. The following sensitivity analyses will be conducted:

- Missing endpoint information (including data obtained after rescue) will be imputed via multiple imputation linear regression approach. A total of 10 imputed datasets will be generated, and the primary efficacy endpoint analysis described below will be carried out on each imputed dataset; the analyses results will be combined across the 10 datasets using the standard techniques for multiple imputed data sets in order to yield overall treatment comparison results on the imputed data.
- Missing endpoint data will also be handled based on the last observation carried forward (LOCF) technique. The last non-missing observation for a subject (i.e., excluding data obtained after rescue) will be carried forward for analysis.
- Data collected after the start of rescue medication will NOT be considered missing, and the primary efficacy endpoint analyses will be performed based on all observed data.

For all other endpoints, the missing data will not be imputed and only the observed data will be used in the analyses.

The number, timing, pattern, reason for and possible implications of missing values in efficacy and safety assessments will be investigated. The dropout patterns may be assessed by graphical methods.

9.1.2 Multiple Comparisons / Multiplicity

The primary objective of this study is to identify the effect of bexagliflozin tablets in three strengths on the placebo-corrected change in HbA1c from baseline after 12 weeks of treatment. All secondary endpoints are considered exploratory and adjustment for multiple endpoints will not be performed.

9.2 Determination of Sample Size

Approximately 320 subjects will be randomized and equally allocated to receive bexagliflozin tablets, 5 mg, 10 mg, 20 mg, or placebo.

The sample size calculation for this study is based on a two group t-test with a two-sided significance at the 5% level and the following assumptions:

- 1) The placebo-corrected population mean change from baseline to Week 12 in HbA1c in the highest dose group of 20 mg will be -0.5%.
- 2) The pooled standard deviation for the change from baseline to Week 12 in HbA1c for the active and placebo groups will be 0.9%.

Under the above assumptions, an estimated sample size of 70 evaluable subjects per treatment arm yields approximately 90% power to detect a treatment difference between bexagliflozin and placebo. A sample size of 80 per arm has been selected to account for a potential drop-out and to allow adequate safety evaluation. The total sample size for this study will be 320 subjects.

This study will be conducted at multiple investigative sites and will likely involve variable numbers of subjects at each site. Enrollment will be on a competitive basis but will be capped at 32 subjects from each site.

9.3 Analysis Populations

9.3.1 Full Analysis Set

All subjects who are randomized, take at least one dose of double-blind study medication, and have at least one post-randomization HbA1c measurement will be included in the Full Analysis Set (FAS). All analyses of the FAS will be based on each subject's randomized assigned treatment.

9.3.2 Safety Analysis Set

All subjects who are randomized and take at least one dose of double-blind study medication will be included in the Safety Analysis Set. Safety analyses will be based on the medication that was actually dispensed to each subject.

9.3.3 Per Protocol Analysis Set

The Per Protocol (PP) Analysis Set will include all subjects in the FAS who meet the study eligibility requirements and have no major protocol deviations that affect the validity of the efficacy measurements. Protocol deviations that may result in subject exclusion from the PP Analysis Set will be detailed in the Statistical Analysis Plan.

9.4 Demographics and Baseline Characteristics

Demographic characteristics include age, gender, race, ethnicity, and study center. Baseline characteristics include baseline HbA1c values, blood pressure, body weight, body mass index (BMI in kg/m^2), fasting plasma glucose level, and prior anti-diabetic treatment status (whether treatment naïve or not). Summary statistics by treatment group will include counts and percentages for discrete variables, and means, SD, Q1, medians, Q3, minimum and maximum for continuous variables.

9.5 Analysis of Efficacy

All efficacy analyses will be performed based on the FAS. The primary endpoint analysis will also be conducted using the PP Analysis Set.

For the primary endpoint of HbA1c change from baseline over 12 weeks of treatment, the MMRM analysis of covariance model (ANCOVA) with baseline HbA1c as a covariate will be fitted to the available data, incorporating all visits at which HbA1c was measured for each subject including the scheduled visits at weeks 2, 6, and 12 as well as the unscheduled visits for measurement of HbA1c (National Research Council, 2010). Treatment, study center, and stratification factor for randomization (treatment naïve versus taking one OHA at baseline) will be applied as fixed effects, as will study week and study week-by-treatment interaction. From this model, an estimate of the treatment difference at week 12 will be generated, as will an assessment of whether this estimate is significantly different when comparing placebo with each dose of bexagliflozin at a two-sided 0.05 level of significance. An unstructured within-patient covariance structure will be assumed. HbA1c values obtained after the start of rescue medication will be excluded from this primary analysis.

The MMRM model is one approach to obtain treatment effect estimates in the presence of missing data. As sensitivity analyses for missing data, the following will be performed:

- 3) Missing HbA1c data (for weeks 2, 6, or 12) will be imputed via multiple imputation (MI), following which the MMRM will be repeated on the complete datasets with results combined across complete datasets using standard MI techniques; HbA1c values collected after the start of rescue medication will be considered missing.
- 4) Missing HbA1c data will be imputed via LOCF, following which the MMRM will be repeated; HbA1c values collected after the start of rescue medication will be considered missing.
- 5) HbA1c values collected after the start of rescue medication will NOT be considered missing, and the MMRM analyses will be re-performed.

For the primary efficacy model, a test for a significant baseline-by-treatment interaction will be performed in a separate model, using a 0.100 alpha level. If the baseline-by-treatment interaction is significant, then the ANCOVA assumptions are violated and an analysis of variance (ANOVA) model will be used instead, omitting the baseline covariate.

A treatment by study center interaction effect will be added to the MMRM ANCOVA (or ANOVA) model used for the analyses of the primary efficacy variable. If a statistically significant treatment by study center interaction effect is noted using a 0.1 level of significance, then separate analyses will be performed for each study center.

In addition to the week 12 comparisons, the change from baseline to week 2 and week 6 will also be analyzed from the same MMRM ANCOVA model using 95% CIs for the between-group mean changes. The secondary efficacy endpoint, changes in HbA1c over time will be assessed descriptively using graphical methods

To examine the dose response, tests for linear and quadratic dose-response relationships between the doses (0 [placebo], 5, 10 and 20 mg bexagliflozin) and the change from baseline in HbA1c at week 12 will be conducted using a general linear model and appropriate orthogonal polynomial contrasts.

Fasting plasma glucose, systolic and diastolic blood pressure, and weight will be analyzed using the same MMRM ANCOVA model used in the primary efficacy analysis.

For each subject, the post-baseline HbA1c values on or before week 12 will be assigned to a category of $< 7\%$ or $\geq 7\%$. Incidences of reduction of HbA1c to $< 7\%$ will be analyzed using a logistic regression model with effects for treatment, study center and baseline HbA1c. Odds ratio and the corresponding 95% CI will also be presented.

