3.2 Research Methods and Procedures

3.2.1 Washout and Run-in Period

Eligible subjects who are not treatment naïve will discontinue their current OHA and enter a 6- or 10-week washout. Those who are taking any OHA except a thiazolidinedione will discontinue the medication for 6 weeks. Subjects who are taking a thiazolidinedione will discontinue the medication for 10 weeks. At the start of the washout, each subject will be provided with diet and exercise counseling, a glucometer, a glycemic control diary in which to record daily fasting self-monitored blood glucose (SMBG) measurements and instructions regarding the appropriate circumstances under which a call to the clinic to register an observation of hyperglycemia should be made (see *Glycemic Control* below). Two weeks after the start of the washout period each subject will participate in a phone interview with study staff for SMBG data review and general safety evaluation. Subjects who remain

eligible at the end of the 6 or 10 week washout period will proceed to a 2-week placebo run-in period. Subjects will be ineligible if they exhibit fasting blood glucose values ≥ 250 mg/dL on two consecutive days during the wash-out period.

Eligible subjects who are treatment naïve will not require a washout period and will proceed to the run-in period. These subjects will be provided with diet and exercise counseling, a glucometer, and a glycemic control diary in which to record daily fasting SMBG measurements at the start of the 2-week placebo run-in period.

Treatment naïve subjects and subjects on background OHA who complete the washout will enter a 2-week single-blind placebo run-in period. Each subject will be provided with placebo run-in drug, dosing instructions, and instructions regarding the appropriate circumstances under which a call to the clinic to register an observation of hyperglycemia should be made (see *Glycemic Control* below). During the run-in, a placebo tablet should be taken daily in the morning prior to eating or drinking; the medication should be taken with water.

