6.13 Appropriateness of Measurements

The percentage of HbA1c is a widely used measure of chronic glycemia, reflecting average blood glucose levels over a 2- to 3-month period of time. It is an accepted surrogate marker for risk of microvascular complications and is widely used as a measurement for the adequacy of glycemic management. Other study procedures and measurements in this protocol are widely used and generally recognized as reliable, accurate, and relevant for subjects with T2DM.

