3.2.2 Definition of Subgroups

Consistency of treatment effects across country (USA versus Japan) will be examined through the addition of a treatment-by-country interaction term to the statistical model for the primary efficacy endpoint. This is described in Section 3.8.1 of the SAP. No other subgroup analyses are planned.

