3.8.1 Primary Efficacy Endpoint(s)

The primary endpoint is HbA1c change from baseline through 12 weeks, and the primary analysis is based on the available data and data obtained after rescue will be excluded and considered missing. Mixed model repeated measures (MMRM) analysis of covariance model (ANCOVA) with baseline HbA1c as a covariate will be fit to the available data, incorporating all visits at which HbA1c was measured for each subject including scheduled visits at Weeks 2, 6, and 12 as well as unscheduled visits for measurements of HbA1c. Treatment (placebo, 5 mg, 10 mg, 20 mg), study center, prior anti-diabetic treatment status, study visit and treatment-by-visit interaction will be applied as fixed effects and subject as a random effect.

A normal distribution will be assumed for the built-in probability distribution. Model assumption will be checked. An unstructured (UN) within-subject covariance structure will also be assumed. The Kenward-Roger approximation will be used to estimate the denominator degrees of freedom.

Sample SAS code for this analysis is as follows:

```
proc mixed data=temp method=reml covtest;  
  class subject visit treat prior center;  
  model change = visit treat prior center baseline visit*treat /  
  solution ddfm=KENWARDROGER;  
  repeated visit / subject=subject type=un;  
  lsmeans visit*treat / diff=all cl alpha=0.05;  
run;
```

In the case that this covariance matrix is not an appropriate estimate, other covariance structures (e.g., compound symmetry) will be considered and ultimately determined through graphical tools (i.e., plot of changes in covariance and correlation among residuals on the same subject over lag between times of observation) and information criteria [e.g., Akaike's Information Criteria (AIC)].

Descriptive statistics will be presented for the observed measurements as well as for change from baseline by treatment group and visit overall (all subjects) and by country.

Least squares (LS) means and the corresponding standard errors (SE) of the change from baseline over time will be presented by treatment. In addition, the time profile of these LS mean and SE values will be presented graphically.

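### The stratification factor enters the primary MMRM as a shift constant over visits; adding a visit-by-stratum term costs two parameters and removes a possible small overstatement (about 0 to 4%) of the Week 12 standard error

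*Protocol*

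**What the plan says.** Protocol 5.4 and SAP 2.2.2 stratify randomisation on one factor, background anti-diabetic treatment status. In the primary model of Protocol 9.5, "Treatment, study center, and stratification factor for randomization (treatment naïve versus taking one OHA at baseline) will be applied as fixed effects", and the only interaction listed is study week by treatment. The sample code in SAP 3.8.1 matches: "model change = visit treat prior center baseline visit*treat". Here `prior` has one coefficient for all visits, and there is no `visit*prior` or `treat*prior` term. The covariance is unstructured.

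Treatment interactions are planned with baseline HbA1c, centre and country (Protocol 9.5; SAP 3.8.1). Descriptive HbA1c tables are overall and by country. SAP 3.2.2, after describing the country analysis, ends: "No other subgroup analyses are planned". The report will therefore show neither a dose effect nor an HbA1c course by stratum.

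On timing, Protocol 3.2.1 says: "Those who are taking any OHA except a thiazolidinedione will discontinue the medication for 6 weeks". Thiazolidinedione users stop for 10 weeks. A 2-week run-in follows. No HbA1c is drawn at V1 (Protocol Appendix 2), so baseline is normally the S5 sample. Protocol 6.13 describes HbA1c as "reflecting average blood glucose levels over a 2- to 3-month period of time".

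**The concern.** A constant shift is the right form only if naïve and washed-out subjects differ by the same amount in change from baseline at every visit. The documents give some reason to doubt this for non-thiazolidinedione users. Their baseline may still reflect weeks on the earlier agent, and HbA1c may go on rising after baseline in every arm. The gap would then be smaller at Week 2 than at Week 12.

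One coefficient cannot follow such a gap. The part of the Week 12 gap that it misses goes into the Week 12 residual variance and so into the reported standard errors of all three dose comparisons. Stratified randomisation balances the arms on this factor, so the true sampling error of the difference does not contain that part.

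What is at stake is a slightly conservative standard error, and a report that does not describe the two patient groups the design deliberately combines.

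**Working it through.** **1. The plan's own figure.** Protocol 9.2 uses a "two group t-test with a two-sided significance at the 5% level", a difference of 0.5 points, SD 0.9 and 70 evaluable per arm.
- SE = 0.9 × √(2/70) = 0.1521, and 0.5/0.1521 = 3.287.
- Power = Φ(3.287 − 1.96) = 90.8% (noncentral t: 90.4%). The stated figure of about 90% is reproduced.

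**2. Time off drug at baseline.** Protocol Appendix 1 puts S2 at week −8 (or −12 for thiazolidinediones) and S5 at week −0.5. S5 is therefore 7.5 (or 11.5) weeks after the agent is stopped. Assume HbA1c weights glucose equally over 2 months (8.7 weeks) or 3 months (13 weeks). The on-drug share of the S5 value is then:

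| Prior agent | 2-month memory | 3-month memory |
|---|---|---|
| Other OHA | (8.7 − 7.5)/8.7 = 14% | (13 − 7.5)/13 = 42% |
| Thiazolidinedione | 0 | (13 − 11.5)/13 = 12% |

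**3. Drift after baseline.** The loss of effect when the earlier agent is stopped is not in the documents; 0.5, 1.0 or 1.5 points is assumed. Counting from randomisation (8 weeks off drug):
- 3-month memory: remaining drift is (5/13) × loss = 0.19, 0.38 or 0.58 points, of which (2/13) × loss = 0.08, 0.15 or 0.23 appears by Week 2.
- 2-month memory: the remaining drift (0.04 to 0.08 for a loss of 0.5 to 1.0) is complete by Week 2, so a constant shift fits.

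**4. Effect on the Week 12 SE, large sample.** The fitted shift is the GLS-weighted mean of the visit-specific gaps. With g = Week 12 gap − shift and p = share washed out, the SE is inflated by k = √(1 + p(1 − p)g²/SD²). Assume p = 0.5, Week 12 SD 0.9, correlation 0.7, and gaps 0.15/0.38/0.38 at Weeks 2/6/12.
- SDs rising 0.4/0.7/0.9: shift 0.10, g = 0.28, k = √(1 + 0.25 × 0.0784/0.81) = 1.012.
- SD 0.9 at every visit: shift = (0.15 + 0.38 + 0.38)/3 = 0.303, g = 0.077, k = 1.001.

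Over the correlation patterns tried, drift of 0.19, 0.38 and 0.58 gives k of at most 1.004, 1.014 and 1.032 with these rising SDs, and under 1.004 with equal SDs. With a 2-month memory k = 1.000.

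**5. Simulation (4 × 80 subjects, dropout about 12%, half washed out).**
- SDs 0.4/0.7/0.9: ratio of reported SEs, planned to visit*prior, 1.001 (no drift), 1.014 (0.38) and 1.032 (0.58). Mean estimates agreed to 0.001.
- SDs 0.3/0.6/0.9, drift 0.2, 0.4 and 0.6: SEs 0.1481 v 0.1474, 0.1505 v 0.1479 and 0.1538 v 0.1475, so about 0.5%, 2% and 4% too large. At drift 0.4 the empirical SD of the estimate was 0.1455 v 0.1460.
- Differential missingness (assumed 30% at Week 12 in washed-out placebo subjects, 10% elsewhere; drift 0.42 to 0.63): the constant shift made the 20 mg effect 0.007 to 0.019 points smaller than visit*prior did.

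**6. Consequence at 4%.**
- At 70 per arm, with true sampling error unchanged: power = Φ(3.287 − 1.96 × 1.04) = 89.4%, against 90.8%.
- At 80 per arm: CI half-width 1.96 × 0.9 × √(2/80) = 0.279 becomes 0.279 × 1.04 = 0.290.

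**7. What a by-stratum result could show.** An even split is assumed.
- 40 per arm per stratum: SE = 0.9 × √(2/40) = 0.201; CI half-width 0.39.
- Difference between strata: SE = √2 × 0.201 = 0.285; detectable with 80% power (1.96 + 0.84) × 0.285 = 0.80.
- 35 per arm per stratum: 0.85. A 30:70 split: 0.87 to 0.93.

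**The case against.** A time-constant covariate effect is a common MMRM specification, and baseline HbA1c is treated the same way in the same code. No passage says that washed-out subjects are off steady state at baseline. Protocol 3.3 gives the washout's purpose as keeping earlier medication from determining the 12-week value. Drift, early-visit SDs and stratum shares are all assumed, and power stays near the planned 90%. A by-stratum analysis could detect only a gap larger than the whole assumed effect of 0.5. Prior status is already adjusted for, and stratum estimates can be produced later from the same data.

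Most of this stands, and it sets the size of the point. It does not make the constant shift the better choice. The endpoint is change from baseline, so protecting the 12-week value does not settle the baseline value. The design itself expects a rise off drug: users of one agent may screen at 6.5% but must reach 7.0% before randomisation. In the SAP's regression imputation, prior status is a covariate in imputing each visit, so the stratum effect may differ by visit there; the MMRM fitted afterwards forces one coefficient.

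A reader might infer three stronger things, none supported:
- *That the dose effects are biased.* The arms are balanced on the stratum and the visit-by-treatment means are free; the estimates agree to 0.001, or within 0.02 under the differential missingness assumed above.
- *That precision is lost.* The empirical SDs (0.1455 v 0.1460) show an equally precise estimator; only the reported SE is conservative.
- *That washed-out baselines are known to be unsettled.* This is plausible for non-thiazolidinedione users with a 3-month memory and weak otherwise.

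**Conclusion.** The point holds as a minor improvement. Two facts are plain in the documents: the only stratification factor is a constant shift over visits in the primary model, and no estimate by stratum is planned. Whether the stratum gap changes after baseline is an inference from the washout length and the stated HbA1c memory.

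If it does change, the reported Week 12 SE may be too large by about 0 to 4% for drift of 0 to 0.6 points, with half the subjects washed out and SDs that rise over visits. The excess is under 1% if the SDs are equal. At the top of the range this costs about 1.4 points of power (90.8% to 89.4%). The type I error rate is not inflated, and no dose conclusion is likely to depend on it. The missing by-stratum result does not depend on the drift assumption, but could only ever be descriptive.

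**What to change.** In Protocol 9.5 and the SAP 3.8.1 text and code, add `visit*prior` to the primary MMRM. With three visits and two strata this is (3 − 1) × (2 − 1) = 2 extra parameters. If there is no drift, almost nothing is lost: the two reported SEs differed by 0.1% in simulation.

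Optionally, fit a separate model that also has `treat*prior*visit` with its lower-order terms, and report the Week 12 dose-minus-placebo differences with 95% CIs within each stratum. Amend SAP 3.2.2 to match, label the result exploratory, and state that the trial is not sized for this interaction (detectable gap about 0.8 points with an assumed even split).

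The cost is one model term and, if wanted, one extra model and one table. The data are already collected. No subjects, visits or procedures are added, and the washout is unchanged.
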